3.1 Background

The COVID-19 pandemic is occurring amid a high prevalence of mental health conditions²² and increasing suicide rates²³ in the United States. Individuals are experiencing anxiety, financial hardship, disruption to school and work schedules, and repeated exposure to information and misinformation in mainstream and social media²⁴ as a result of the pandemic. This may increase their risk of suicide either directly or through proximal risk factors and can lead to or exacerbate other mental health conditions.²⁵⁻³⁶

Mental health conditions are common in the United States, and in 2017 nearly 1 in 5 adults ages 18 and older reported a mental illness in the last 12 months.²² In adolescents ages 13-18 years, diagnostic interview data showed nearly 1 in 2 reporting lifetime prevalence of any mental disorder with anxiety disorders being the most common (31.9%).³⁷ An increase in social isolation and loneliness are likely to be significant adverse consequences of the pandemic²⁵, particularly in elderly individuals³⁸ and adolescents.³⁹ Both social isolation and loneliness are associated with anxiety, depression, self-harm, and lifetime suicide attempts.^{40,41} Additionally, a number of the anticipated consequences of quarantine

and social and physical distancing measures introduced to prevent community spread of the disease are themselves risk factors for mental health issues²⁵ including self-harm, alcohol and substance misuse, domestic and child abuse and psychosocial risks (i.e. social disconnection, loss of income, and feeling a burden).^{25,42} Nearly 41% of 5,470 US adults who completed a web-based survey in late June 2020 reported adverse mental or behavioral health conditions with essential workers, young adults, unpaid caregivers, and racial/ethnic minorities being disproportionately affected.⁴³ **The prevalence of anxiety disorder symptoms was 3x higher than reported in 2019 and depression was 4x higher.**⁴³

Suicide is a leading cause of death in the United States and one of only three leading causes of death that is on the rise.²³ Suicide rates have risen by over 30% in more than half of US states since 1999, with Mid-Western and Intermountain West States in particular exhibiting alarmingly high increases in suicide rates.²³ Idaho's suicide rate is the sixth highest in the US, 50% above the national average.²³ In 2016, nearly 45,000 individuals in the U.S. died by suicide,²³ roughly equivalent to one suicide every 12 minutes. In the COVID-19 era, approximately 11% of adults reported seriously considering suicide in the past 30 days, and the percentage was significantly higher among 18-24-year-old respondents (25.5%).⁴³ **Half of suicide decedents seek healthcare – often in EDs or primary care settings – within a month of their death.**⁴⁴

Healthcare providers and staff face additional stress due to their increased exposure to infected patients^{45,46} and the burden of bearing witness to the devastating effects of this disease. Healthcare workers who are younger, female, parents to dependent children, or report pre-existing psychological or physical ill health are more vulnerable to mental distress when caring for patients during a viral outbreak.^{45,46} Interventions that support frontline staff's mental well-being are needed to mitigate the added psychological distress during a pandemic. Health systems have an obligation to address mental distress and risk factors for suicidal ideation and behavior in the patient populations they serve and in clinicians and staff they employ.

Experts worldwide and at St. Luke's Health System (SLHS) have called for research to (1) better understand the mental health impact of COVID-19 on the general population, and key populations including healthcare providers and staff, older adults, and adolescents,^{25,28} **and (2) to determine the best evidence-based mental health interventions that can be delivered virtually at scale with minimal resources during the COVID-19-era.**^{25,27,28} Additionally, the Patient-Centered Outcomes Research Institute (PCORI) has called for research using a comparative effectiveness framework that can provide timely answers to COVID-19-related challenges facing health systems, patients, caregivers, and clinicians.⁴⁷ as well as research related to suicide prevention in adult and adolescent patients.⁴⁸

Caring Contacts is an evidence-based suicide prevention intervention and one of the only brief suicide prevention interventions that has demonstrated effectiveness in reducing suicidal ideation and behavior in randomized clinical trials.⁴⁹⁻⁵¹ Caring Contacts has been recommended as part of standard care for

MHAPPS Trial Protocol
SLHS Applied Research
December 30,2020

suicide prevention by the Joint Commission,⁵² the US Department of Veterans Affairs (VA),⁵³ the US Department of Defense,⁵³ and the National Action Alliance for Suicide Prevention.⁴⁴ A recent high-quality trial demonstrated a 44% reduction in the odds of suicidal ideation and a 48% reduction in the odds suicidal behavior among veterans receiving Caring Contacts compared to a control group.⁵¹

Caring Contacts aim to make individuals feel supported and cared for, typically consisting of brief messages sent via letters^{49,50} and postcards,^{54,55} emails⁵⁶ or text messages^{51,57} from a provider to a patient. Caring messages are non-demanding expressions of care for a person's well-being and a reminder that help is available.^{50,51,56,58} This study will use a text messaging platform to deliver Caring Contacts which will be cost-effective and low burden to participants and staff, sending 11 pre-scripted messages scheduled over a 6-month timeframe. Trained follow-up specialists at the Idaho Suicide Prevention Hotline (Hotline) will correspond with individuals who choose to respond to the text messages, although it is never required or expected of the participants to respond. Mobile technology-based health interventions can be useful to help alleviate unmet mental health service needs in low-resource settings and marginalized populations such as minorities and people with limited income.⁵⁹⁻⁶¹

The proposed study will address several key gaps in the scientific literature. While the effect of Caring Contacts on suicidal ideation and behavior is well documented, **its effect on other types of mental distress including depression, anxiety and psychological stress has not been rigorously studied**, particularly in civilian populations post-crisis or who have not been discharged with a recent suicide attempt.

The theoretical basis for Caring Contacts and its hypothesized causal mechanism are both related to loneliness or a lack of social connection.⁶² The Caring Contacts intervention provides recipients with messages meant to reinforce the idea that someone cares about them, is thinking of them, and expects nothing in return. The messages facilitate a feeling of caring but also serve as a gentle reminder that support and resources are available. A recent meta-analysis of causal mechanisms for brief contact interventions such as Caring Contacts affirms that social support is the most commonly reported mechanism through which these interventions affect suicidal ideation and behavior.⁶³ **Loneliness is a well-established risk factor for suicide,^{15,62} depression,^{36,64-66} psychological stress,^{66,67} and anxiety.^{36,64,66}** We therefore hypothesize that by reducing loneliness, Caring Contacts may also reduce depressive symptoms, stress, and anxiety, in addition to reducing suicidal ideation and behavior.

The cross-sectional survey (Aim 1) will provide timely data on the prevalence of mental distress among patients, providers, and staff in the COVID-19 era in a largely rural state. The comparative effectiveness trial (Aim 2) will contribute to filling the literature gap regarding whether non-demanding brief contact interventions such as Caring Contacts are effective in supporting individuals struggling with non-suicidal mental distress.

3.2 Significance

The COVID-19 pandemic has dramatically impacted individuals and communities, with implications for both mental and physical health.^{25-28,68} **There is an urgent call for research to collect data on mental health effects of the COVID-19 pandemic across vulnerable groups and the population as a whole²⁵ and how mental health consequences can be mitigated under pandemic conditions.**²⁵ Additionally, providers need actionable research to determine the best evidence-based mental health interventions that can be delivered virtually at scale with minimal resources during the COVID-19 era.^{25,27,28} St. Luke's Health System leadership is supportive of this research and has encouraged the inclusion of providers and employees in key study populations.

The proposed research fills key gaps in evidence and is aligned with PCORI research priorities. This study will describe the extent and character of mental distress and risk factors for suicide on key populations in the COVID-19 era. Study participants will include healthcare clinicians/staff and patients, both adult and adolescent, from a private non-profit health system. This would be the first published data comparing the effectiveness of two versions of the Caring Contacts intervention (one with an introductory phone call followed by text messages (CC+) and without an introductory phone call (CC)) with individuals who report loneliness or other mental distress including anxiety, depression, stress, emotional dysregulation, and low health-related quality of life.

This study will provide high-quality data collected with scientific rigor to determine whether CC+ or CC more effectively improves mental health outcomes and suicide risk factors among health care providers and staff, and adolescents and adults in primary care settings. **Additionally, this will be the first randomized controlled trial to study the effects of the Caring Contacts model to support individuals with non-suicidal mental distress.** The study population will include both urban and rural residents in a state with a high prevalence of suicide,²³ including a rural county with one of the highest infection rates of COVID-19 in the U.S.⁶⁹

This pragmatic study is designed to optimize dissemination and implementation potential and scalability. The intervention design capitalizes on technology and will be delivered in partnership with an established community resource (Idaho Suicide Prevention Hotline) that will reach urban and rural populations. This approach will allow the health system to consistently deliver an effective brief social supportive intervention without requiring any human resources from health system providers and staff responding to COVID-19 demands. **This models a health system-community based partnership that could be realistically replicated and brought to scale by other clinics and health systems faced with similar strains on resource and workforce capacity, including those serving rural populations.** We will partner with the Idaho Suicide Prevention Hotline to disseminate results of this study via the national network of Suicide Prevention Hotlines, which regularly liaise with health systems nationwide.

This study will have immediate and enduring public health impact, allowing health systems and community partners in Idaho and nationally to select the best brief, virtual, evidence-based intervention to provide mental health support. The interventions being compared are feasible to implement at scale even while quarantine and/or social and physical distancing measures are in effect from the pandemic, including in low-resource settings with limited access to behavioral health services.

4. Research Methods

4.1 Study Design

4.1.1. Aim 1: Cross Sectional Survey

Aim 1 is a cross sectional survey of patients, providers, and staff to measure the prevalence of various measures of mental distress in the context of the COVID-19 pandemic.

4.1.2 Aim 2: Comparative Effectiveness Trial

Aim 2 (primary analysis) is a randomized controlled trial comparing the effectiveness of CC+ vs. CC. The study objectives, outcomes, and interventions all pertain to the individual level.

4.2 Randomization

Randomization will occur at the individual level. A list of potentially eligible participants will be generated based on responses to the survey conducted through Aim 1. Survey respondents reporting elevated mental distress will be part of the potentially eligible study population for Aim 2. Statistical software will be used to randomly assign Aim 2 participants to an intervention arm immediately following informed consent and study enrollment.

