5.4 Populations for Analyses

Analyses will be completed using the following populations:

1. **Intention to Treat (ITT) Analytic Population:** Data for all participants that complete study enrollment will be included in this dataset.
2. **Safety Analysis Population:** The dataset shared with the Data & Safety Monitoring Board for safety analysis will include data for all participants who completed study enrollment (e.g., the ITT Analytic Population Dataset).
3. **Per-Protocol Analysis Population:** Data for a subset of participants who were retained for the full study, were sent all 11 caring text messages, and received a phone call if randomized to the CC+ intervention (as outlined in protocol section 9) will be included in this dataset.
4. **Additional populations:** Additional datasets may be developed to complete sensitivity analyses, for example, where missing data have been imputed using different techniques.

6. Study Procedures

Aim 1: Cross Sectional Survey (Email REDCap survey link for providers and staff; send REDCap survey link via MyChart or email for patients)

- Aim 1 study enrollment and informed consent
- Aim 1 Survey
 - Demographics questions
 - C-SSRS (suicide risk)
 - NIH Toolbox Social Relationship Scales (loneliness, stress)
 - INQ (defeat, entrapment, perceived burdensomeness, and thwarted belongingness)
 - PHQ-9 (depression)
 - GAD-7 (anxiety)
 - COVID-19 beliefs and practices survey (brief)

Aim 2: Baseline / Enrollment (Subset of Aim 1 participants; see below)

- Aim 2 study enrollment and informed consent (phone call with Research Coordinator or study staff to complete via REDCap)
- Aim 2 Baseline assessments (Email or text REDCap survey link)
 - Baseline survey (Socio-economic status, gender identity, sexuality, religion, and alcohol and illicit drug use)
 - Expanded COVID-19 beliefs and practices survey (additional questions related to impact of COVID-19 on the individual, and his/her/their family, friends, and community)
 - Contact Sheet to collect alternative forms of contact for study participant

Aim 2: Caring Contacts Interventions (see description of interventions in section 9)

- **CC+:** 1 call, within 2 weeks of enrollment, and 11 caring text messages, sent from Hotline

follow-up specialists according to a standardized schedule over a 6-month period

- **CC:** 11 personalized caring text messages sent from Hotline follow-up specialists according to a standardized schedule over a 6-month period

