8.3.5 Alcohol and Illicit Drug Use

Alcohol and illicit-drug use will be measured at baseline and 6 months with questions adapted from the Youth Risk Behavior Survey.¹⁰⁷ Additional questions will be included to measure self-reported changes in alcohol or illicit-drug use since the beginning of the COVID-19 pandemic.

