12.2 Data Management

This study will employ a comprehensive data management plan. The results from the screening and baseline questionnaires (as well as informed consent documents) will be directly entered in REDCap. The patient will be assigned a unique identifier and randomly assigned to one of the two intervention arms immediately following informed consent and study enrollment. Follow-up specialists at the Hotline will review records of new participants and follow-up with patients to initiate the CC+ or CC intervention. Hotline staff will record any attempt at contact or successful contact made.

The statistics team will compile all data for each participant from REDCap on a routine basis for reports and to build and maintain a complete dataset. To protect the confidentiality of participants, data and associated documentation will be available to the PI of the study and key personnel only, under a data-sharing agreement that includes a commitment to: (1) use the data only for research purposes, (2)

secure the data using appropriate computer technology, (3) destroy or return the data after analyses are completed, and (4) not further distribute the data outside specified members of the research team in compliance with SLHS Research data privacy and sharing practices and policy.

The University of Washington Institute of Translational Health Sciences (ITHS) hosts REDCap, a secure, HIPAA-compliant web application, which will be used for building and managing online surveys and databases for this research. ITHS provides REDCap support and an array of research data curation and storage support. Other databases (such as Access, Excel) may be used for study management purposes; all such data will be kept on secured, password-protected computers.

13. Statistical Analysis

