4.1 Data Management

This study will employ a comprehensive data management plan. The results from the screening and baseline questionnaires (as well as informed consent documents) will be directly entered in REDCap. Participants will be assigned a unique identifier; Aim 2 participants will be randomly assigned to one of the two intervention arms during the informed consent process just prior to study enrollment. Follow-up specialists at the Hotline will record any attempt at contact or successful contact made. The statistics team will compile data for each participant from REDCap on a routine basis for reports and to build and maintain a complete dataset.

The University of Washington Institute of Translational Health Sciences (ITHS) hosts REDCap, a secure, HIPAA-compliant web application, which will be used for building and managing online surveys and databases for this research. ITHS provides REDCap support and an array of research data curation and storage support. Other databases (such as Access, Excel) may be used for study management purposes; all such data will be kept on secured, password-protected computers.

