6.3 Exploratory endpoints

- Suicide attempts and lethal means will be summarized and compared across treatment arms. Questions will include the number of attempts and aborted attempts and lethal means.
- Psychological stress will be measured using the NIH Toolbox and assessed as change from baseline. This instrument results in a continuous T-score outcome.
- Changes in alcohol and illicit drug use will be described. Participants will be asked if they are current, ever, or never user of a variety of substances (tobacco, alcohol, marijuana, other illicit drugs), as well as the amount and frequency of use for current users. Participants will be asked about whether or not the amount they use has changed. Changes from baseline to 6 months in the current/ever/never question will be summarized for each substance, as well as reporting the number and percentage of participants with any increase or any decrease.
- The GAD-7 scale will be used to measure anxiety. Participants respond to seven items and receive possible scores of 0-21.
- Attendance at mental healthcare appointments will be measured as a dichotomous variable (yes/no) at 6 months through self-report.

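### The plan does not require the Aim 2 baseline survey before randomisation, so baseline alcohol and drug use can be reported after assignment and, in CC+, after the introductory call

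*Protocol*

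**What the plan says.** **Time of assignment.** Protocol 4.2: "Statistical software will be used to randomly assign Aim 2 participants to an intervention arm immediately following informed consent and study enrollment". Protocol 12.2 repeats the rule: "randomly assigned to one of the two intervention arms immediately following informed consent and study enrollment". SAP 4.1 differs: "randomly assigned to one of the two intervention arms during the informed consent process just prior to study enrollment".

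**Enrolment and survey as separate steps.** Protocol section 6 lists first "Aim 2 study enrollment and informed consent (phone call with Research Coordinator or study staff to complete via REDCap" and then, as its own item, "Aim 2 Baseline assessments (Email or text REDCap survey link". Protocol 16.2.2 also counts them separately, at 30 and 20 minutes.

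**Schedule.** Protocol Table 1 puts consent, the baseline survey with contact sheet, and randomisation all at 0 weeks. The survey row is printed above the randomisation row. The CC+ call is at 0-2 weeks, and Protocol 9.1 allows it at any time in the two weeks after enrolment.

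**Masking.** Protocol 4.3 says that participants cannot be masked.

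**Use of the baseline.** Protocol 8.3.5: "Alcohol and illicit-drug use will be measured at baseline and 6 months". SAP 6.3: "Changes from baseline to 6 months in the current/ever/never question will be summarized for each substance". Drug/alcohol use is also a potential effect modifier in Protocol 13.1 and SAP 6.5.

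**The concern.** A baseline supports a comparison of change only if it is measured before anything that differs between the arms. Here a participant may finish the consent call, be assigned, and answer the linked survey days later. In CC+ the introductory call may have taken place in between. Protocol 9.1 says that this call reviews the person's distress and discusses helpful resources, which could make someone more, or less, willing to report drinking or drug use. No such call exists in CC.

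Two analyses are exposed:

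- **Change in alcohol and drug use.** A shift in the CC+ baseline alone moves the between-arm difference in change, even if use at 6 months is the same in both arms.
- **Drug/alcohol use as an effect modifier.** If the call changes who reports current use in CC+, groups defined by that report are no longer comparable between arms. An apparent interaction could then reflect reporting.

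No planned analysis would detect or correct either problem.

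**Working it through.** **Step 1: is survey-first required anywhere?**

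| Place | What it fixes |
|---|---|
| Protocol 4.2, 12.2 | Assignment directly after consent and enrolment; survey not named as a condition |
| SAP 4.1 | Assignment during consent, before enrolment; survey not named as a condition |
| Protocol 6 | Survey is a separate link; no return window |
| Protocol Table 1 | Survey and randomisation share one time point; row order suggests survey first but states no rule |
| Protocol 9.1 | Call window opens at enrolment; survey not mentioned |

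No place makes assignment or the call depend on a submitted survey. The protocol and SAP also disagree on whether assignment falls before or after enrolment.

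**Step 2: which baselines come from this survey?** From Protocol Table 2:

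- Loneliness, C-SSRS, INQ-15, stress, PHQ-9 and GAD-7: Aim 1 survey, so before Aim 2 consent. Not affected.
- Alcohol and drug use: Aim 2 baseline survey and outcome survey only. The Aim 1 objective mentions substance use, but neither the Aim 1 survey list in Protocol section 6 nor Table 2 places these questions in the Aim 1 survey. Affected.
- Outpatient mental health service use: Aim 2 baseline and outcome surveys. Protocol 8.3.9 and SAP 6.3 analyse it as yes/no at 6 months, so there is no change contrast to bias.
- Gender identity, sexuality, religion and domestic violence: also from the Aim 2 baseline survey. The first three are unlikely to move with assignment or one call. Domestic violence is not an outcome, a named modifier or a listed subgroup.

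**Step 3: how large could the bias be?** The plan gives no figure to reproduce and no survey return times, so the following are assumptions:

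- the call falls evenly over 0 to 14 days after enrolment, and everyone in CC+ receives it;
- the survey is returned evenly over 0 to *w* days, independently of the call;
- after the call, reported current use shifts by *s* percentage points.

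The share of CC+ surveys that follow the call is *f* = (mean return time)/14 = (*w*/2)/14. The CC share is 0. The CC+ baseline moves by *f* × *s*, and the between-arm difference in change moves by the same amount with the opposite sign.

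| Survey returned within | *f* | Bias, *s* = 5 points | Bias, *s* = 10 points |
|---|---|---|---|
| At enrolment | 0 | 0 | 0 |
| 1 day | 0.5/14 = 3.6% | 0.18 | 0.36 |
| 3 days | 1.5/14 = 10.7% | 0.54 | 1.07 |
| 14 days | 7/14 = 50% | 2.5 | 5.0 |

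CC+ participants who are never reached would lower *f*. Any effect on answers of merely knowing the arm is not counted.

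**The case against.** The strongest reply is that survey-first is what the authors intend. Table 1 prints the survey above randomisation at 0 weeks, ahead of the call window. Protocol section 6 groups the survey with enrolment. Protocol 5.3 provides the contact sheet, which is part of the same package, at enrolment. Protocol 12.2 mentions the baseline questionnaires before it mentions assignment. The flow diagram is not available to settle the matter.

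This stands in part. A reader might infer that randomisation always precedes the survey, and the documents do not establish that. They leave the order open, and the sections that state when assignment occurs do not mention the survey. Row order within one time point is not a rule. If survey-first is intended, Protocol 4.2 and 12.2 and SAP 4.1 still need to say so.

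It is also fair that 2.5 points is close to a worst case under the 5-point assumption. Returns spread over 14 days fit poorly with a survey scheduled at 0 weeks, and prompt returns bring the figure down to a few tenths of a point.

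Two wider readings are tempting and do not hold. The first is that the primary comparison is contaminated. It is not, because SAP 7.2.1 adjusts for baseline loneliness, which comes from the Aim 1 survey. The second is that change in service use is biased. No such change is analysed. Separately, SAP 5.3 requires a completed baseline survey for its intention-to-treat set. That concerns who is analysed, not the timing of baseline values, and it adds no weight here.

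**Conclusion.** The point holds in a limited form. As written, the plan allows the only baseline for alcohol and drug use to be reported after assignment by unmasked participants and, in CC+, after the call. The exposed results are the change in substance use and the use of drug/alcohol use as an effect modifier. The SAP treats the former as exploratory and descriptive, although Protocol 8.3 lists substance use as a secondary outcome.

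The size is not known. With a 5-point reporting shift and calls spread evenly over 14 days, the bias runs from zero (survey done at enrolment) through about 0.2 and 0.5 points (returns within 1 and 3 days) to 2.5 points (returns over the full 14 days). It scales directly with the assumed shift, for which the documents give no value. This is a cheap improvement worth making, and it does not threaten the primary analysis.

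**What to change.** Reconcile Protocol 4.2, section 6, 12.2, Table 1 and SAP 4.1 to one order: consent, Aim 2 baseline survey, randomisation, first intervention contact from the Hotline. Have REDCap release the assignment only once the survey is submitted, ideally during the consent call. This governs assigned-intervention contacts only and leaves the safety contacts in Protocol 6.2 as they are.

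The cost is a wording change and a REDCap rule. Consenters who do not complete the survey would not be randomised and would have to be replaced. The documents give no basis for estimating how many. Assignment may also be slightly delayed for those who do not finish on the call. Completing the survey on the call limits both losses but lengthens the call by the 20 minutes that Protocol 16.2.2 allots to it.

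If anyone has already been randomised under the current wording, compare survey submission times, if REDCap keeps them, with the call times that Protocol Table 2 says are recorded. Report the share of CC+ surveys that came after the call.
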